## **Study Protocol**

The study was designed as a single-blind, prospective, randomized controlled study with a 2-month follow-up period, carried out in rheumatology outpatient clinic, between March 2017 - January 2019. SSc patients who fulfilled the *American College of Rheumatology* (ACR) 2013 criteria with an OA of <40 mm were included in the study. All patients were previously undergone dental examination by a dentist to exclude oral manifestations and dysfunction of temporomandibular joint that may interfere with attempts to exercise. Patients with missing teeth, dysfunction of temporomandibular joints, oral malignancy, recent dental procedures, multiple active digital ulcers and diagnosed psychiatric conditions were excluded. The study has been approved by the local ethical committee (10.06.2016; protocol number:54) and the written informed consent was taken from all the patients included in the study.

Patients' sociodemographic properties were recorded at the first visit. Disease duration was calculated from the first manifestation of the disease. The severity of the disease was evaluated by Medsger's disease severity scale. Patients were randomly divided into two groups. Randomization was done as the sealed envelope method. After the informed consent was taken, the opaque envelope that the patient have chosen was opened and patients were offered the allocated treatment regimen. Group 1 was given exercise regimen and oral hygiene care advices for the first one month; followed by no exercise but oral hygiene care advices for the next four weeks. Group 2 received oral hygiene care advices for the first one month, followed by the exercise regimen twice a day along with oral hygiene care advices for the next four weeks . Oral care advices were given to every participant by a dentist involved in the study at their first visit. The reason of this design aims to increase the sample size to be analyzed receiving exercise treatment, since scleroderma caused microstomia is a rare condition. The exercise program was demonstrated to patients by a clinician at the first visit and given to all patients printed as a manual to be done every day for one month duration of the exercise program. Additionally, a diary was given to patients to mark when they have completed the exercise and to note in the case of pain on daily basis. The exercise regimen was developed on the basis of previous studies and clinical knowledge.

Patients' OA was measured at baseline, 1-month, and 2-months by an experienced dentist at the faculty of dentistry. All the measurements were done by the same dentist who is blind to the exercise regimens to provide consistency. The OA was measured using the interincisal distance between the maxillary and mandibular central incisors in the midline. Patients were asked to open their mouth as wide as they could in the natural head position. The linear distance from the incisal edge of the upper central incisor to the incisal edge of the lower central incisor was recorded using a dental bow compass and measured using a millimeter ruler. Each subject was measured three times every two minutes and the highest value of these three measurements was recorded.

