#### *Statistical analysis*

The IBM SPSS Statistics version 20.0 software package was used for analysis. Categorical variables are expressed as numbers and percentages, whereas continuous variables are summarized as mean and standard deviation and as median and minimum- maximum where appropriate. To compare categorical variables between the groups the chi-square test was used. The Shapiro-Wilk test was used to confirm the normality of distribution for continuous variables. For the comparison of continuous variables between two groups, the Student t test or Mann-Whitney U test was used depending on whether the statistical hypotheses were fulfilled. To evaluate the change in OA measurements obtained in the time interval and to compare the trend in OA measurements between groups, the Repeated Measurements Analysis was applied. The level of  $p<0.05$  was considered as statistically significant.

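### The plan does not say which OA reading decides the <40 mm entry rule; if it is the baseline reading, change from baseline is biased towards improvement, though the randomised comparison is not

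*Combined protocol and SAP*

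**What the plan says.** - Entry (Study Protocol): patients meeting "2013 criteria with an OA of <40 mm were included in the study".
- Measurement (Study Protocol): "OA was measured at baseline, 1-month, and 2-months by an experienced dentist at the faculty of dentistry". No screening OA reading is described.
- Pre-entry examination (Study Protocol): "All patients were previously undergone dental examination by a dentist to exclude oral manifestations and dysfunction of temporomandibular joint". OA is not mentioned as part of it.
- Assessor and recorded value (Study Protocol): "All the measurements were done by the same dentist who is blind to the exercise regimens to provide consistency", and "Each subject was measured three times every two minutes and the highest value of these three measurements was recorded".
- Control period (Study Protocol): "Group 2 received oral hygiene care advices for the first one month, followed by the exercise regimen twice a day". Group 1 does the reverse, with exercise first.
- Analysis (Statistical analysis): a repeated-measures analysis with two aims. The first is "To evaluate the change in OA measurements obtained in the time interval"; the second compares the trend between the groups. Significance is p<0.05.

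The documents give no sample size, OA mean, SD or retest reliability, and do not discuss regression to the mean.

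**The concern.** A one-sided entry threshold on a variable measured with error selects, near the cut-off, patients whose reading was low by chance and turns away those whose reading was high by chance. If the selecting reading is also the baseline, the next reading is higher on average even when nothing has changed.

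That matters here because change over time is one of the two stated aims of the repeated-measures analysis. A significant time effect, or Group 1's first-month gain in millimetres, could come partly or wholly from the entry rule.

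The artefact is also uneven. Group 1's exercise month starts from the selected reading, and Group 2's starts from the month-1 reading, which selected nobody. The Study Protocol says the delayed-exercise design is meant to enlarge the exercised sample available for analysis. If before-after exercise changes from the two groups were set side by side or pooled, the same true effect would look larger in Group 1.

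**Working it through.** The plan has no figure of its own to reproduce. From the documents come the threshold (40 mm, truncation from above), three visits, two randomised groups and alpha 0.05. Everything else below is an assumption.

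**Expected untreated rise if baseline decides entry.** Let mu and SD describe OA in the clinic population from which patients are drawn, r be the visit-to-visit correlation, and z = (40 - mu)/SD. Then

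E[second - first | first < 40] = (1 - r) x SD x phi(z)/Phi(z),

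which is positive for any r below 1.

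- Low end (mu 32, SD 6, r 0.98): z = 1.33; 0.02 x 6 x 0.164/0.909 = 0.02 mm.
- Middle (mu 36, SD 8, r 0.90): z = 0.5; 0.10 x 8 x 0.352/0.691 = 0.41 mm.
- Threshold at the mean (mu 40, SD 8, r 0.90): z = 0; 0.10 x 8 x 0.399/0.5 = 0.64 mm.
- High end (mu 44, SD 8, r 0.80): z = -0.5; 0.20 x 8 x 0.352/0.309 = 1.8 mm.

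**False-positive rate of the time test.** Simulated 2-group x 3-visit repeated-measures ANOVA, 20 per group, no true change:

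| mu (mm) | SD (mm) | r | spurious rise (mm) | time test |
|---|---|---|---|---|
| 32 | 6 | 0.95 | 0.05 | about 5% |
| 36 | 8 | 0.98 | 0.08 | about 6% |
| 32 | 8 | 0.95 | 0.12 | about 6% |
| 36 | 8 | 0.95 | 0.20 | about 7% |
| 40 | 8 | 0.90 | 0.64 | about 20% |
| 44 | 8 | 0.85 | 1.37 | about 52% |

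Group-by-time rejection stays at about 5% throughout. With a separate baseline reading, the time test returns to about 5%. The last row is not a ceiling: r = 0.80 at the same mean and SD gives a larger rise and a higher rate.

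**Check with the plan's highest-of-three rule.** A second simulation recorded the highest of three readings per visit (between-patient SD 7 mm, visit SD 1-3 mm, reading SD 1 mm, mean 32-40 mm, 15 or 25 per group).

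- Pooled baseline-to-month-1 change: false positives 5% to 43%.
- Between-group comparison of that change: 4.5% to 5.6%.
- Month-1-to-month-2 change: about 0.00 mm, false positives 4.3% to 5.5%.
- Mean 36, visit SD 2, 15 per group: 0.34 mm and 8.6% with one shared reading; 0.00 mm and 5.0% with a separate baseline.

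**Precision from a second pre-treatment reading.** Let r1 be the correlation between the two pre-treatment readings and r2 that of each with follow-up. The residual variance, relative to adjusting for one reading, is

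[1 - 2 x r2^2/(1 + r1)]/(1 - r2^2).

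- r1 = r2 = 0.80: 0.802, equivalent to 1/0.802 - 1 = 25% more patients. At 0.95: 0.763, or 31%.
- r1 = 0.90, r2 = 0.80: (1 - 1.28/1.90)/0.36 = 0.906, or 10%.
- r1 = 0.90, r2 = 0.70: (1 - 0.98/1.90)/0.51 = 0.949, or 5%.

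**The case against.** **The double use of one reading is inferred.** A reader might conclude that the plan sets entry and baseline from the same reading. The documents do not say so. All patients had a dental examination before entry, and an OA value could have been taken then. This stands: the supportable statement is that the deciding reading is unspecified, and that only one pre-treatment reading is described.

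**Randomisation protects the efficacy test.** A reader might infer that the trial's treatment comparison is biased. It is not. Both groups pass the same rule, the artefact cancels in expectation at each visit, and Group 2's exercise-free month is a concurrent display of any untreated rise. This stands fully. What remains exposed is the pooled time effect and uncontrolled change from baseline.

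**The size is not in the documents.** Quoting only the inflated rates would mislead. The 52% case needs a clinic mean of 44 mm, so that only about 31% would pass the rule, and a visit-to-visit SD of 8 x sqrt(0.15) = 3.1 mm. One blinded dentist, a fixed landmark and the highest of three readings all argue for good repeatability, and milder assumptions give near-nominal error. This stands, with one limit: repeat readings minutes apart reduce reading error but not day-to-day variation, so they do not remove the effect.

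**The efficiency argument is easily overstated.** A gain of 25% to 31% requires the pre-to-follow-up correlation to equal the correlation between the pre-treatment readings. Variable response to exercise would lower the former. This stands, so no fixed gain should be claimed.

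**Conclusion.** The concern holds conditionally. The plan leaves open which OA reading decides entry. If baseline does, the planned test of change over time and Group 1's baseline-to-month-1 gain are biased towards improvement. The direction follows for any imperfectly repeatable reading; the size cannot be derived from the documents and ranges from negligible to substantial. It grows as the clinic mean approaches or exceeds 40 mm and as repeatability falls. The point does not undermine the randomised comparison. It is a correctable weakness in a secondary strand of inference, and worth correcting because the plan gives nothing that would rule out the larger values.

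**What to change.** 1. State which OA reading decides the <40 mm rule.
2. Take an OA reading by the protocol's own method at the existing pre-entry dental examination, and apply the rule to that reading only.
3. Take a fresh baseline reading with no threshold. Use it as the first visit in the repeated-measures analysis, and keep every patient who qualified, including those whose fresh reading is 40 mm or more.
4. Base the efficacy conclusion on the between-group comparison adjusted for pre-treatment OA. Both pre-treatment readings, or their mean, can be the covariate; the added precision may be modest.
5. If no separate baseline reading exists, report within-group change from baseline as descriptive and show Group 2's first-month change beside Group 1's. This needs no new data.

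The cost is a few minutes at an examination patients already have and a few sentences of text. Some analysed baselines will be 40 mm or more, and the change from baseline will look slightly smaller.

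### Does letting each patient pick a sealed envelope, with no log or no-reuse rule described, undermine the randomisation?

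*Combined protocol and SAP*

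**What the plan says.** Allocation is described in a few sentences of the Study Protocol section of the combined protocol and SAP. "Patients were randomly divided into two groups", and "Randomization was done as the sealed envelope method". The order of events is explicit: once consent had been given, "the opaque envelope that the patient have chosen was opened and patients were offered the allocated treatment regimen". The sentences that follow describe each group simply as having had its regimen. Group 1 exercises in the first month. Group 2 has oral hygiene advice first, "followed by the exercise regimen twice a day along with oral hygiene care advices for the next four weeks".

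The same section covers measurement: "All the measurements were done by the same dentist who is blind to the exercise regimens". OA is recorded at baseline, 1 month and 2 months. The Statistical analysis section evaluates change in OA over time and adds that "to compare the trend in OA measurements between groups, the Repeated Measurements Analysis was applied". It names no analysis population.

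The documents do not mention envelope numbering, who prepared or held the envelopes, a log, whether opened envelopes left the pool, or what followed a declined offer. They give no sample size, allocation ratio or envelope count.

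**The concern.** In the usual sealed-envelope scheme the envelopes are numbered, the next number is opened, and the opening is logged. A reader can then check that each patient received the allocation due at that point and that every opened envelope is accounted for. Free choice from a pool does not allow that check unless a log is kept.

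The word for what happens after opening adds to the unease. A regimen that is offered can be declined, and the text does not say what happens then. If a patient who drew delayed exercise could draw again, or could leave and drop out of the analysis, the groups would no longer be a purely random split. Patients keen to start exercising would collect in Group 1. If they also tended to improve more, for instance through better adherence, the between-group comparison would favour early exercise for reasons unrelated to the exercise. The blinded dentist protects the OA measurement but has no influence on who enters which group.

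**Working it through.** The plan states no figure on this point, so there is nothing to reproduce. The check has three parts.

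**1. What the stated rule does if followed literally.** One consented patient picks one sealed, opaque envelope, it is opened, and that regimen is delivered. Sealing, opacity and opening after consent hide the allocation until the patient is committed. A pick from a mixed pool can be random, and it leaves no fixed next envelope to foresee. Group membership is then a valid random split.

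**2. How large a departure would have to be.** Let f be the share of patients who would refuse Group 2, and d their difference from other patients in the outcome being compared, in SD units. Neither is in the documents; both are assumptions. With independent 1:1 draws, bias = d × (share of refusers in Group 1 − share in Group 2).

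- Re-draw until Group 1. Every refuser ends in Group 1, so the share there is f / (f + (1 − f)/2) = 2f/(1 + f), and it is 0 in Group 2.
- One re-draw. Three quarters of refusers end in Group 1 and one quarter in Group 2. The difference in shares is 1.5f/(1 + f/2) − 0.5f/(1 − f/2).
- Decline, leave and go unanalysed. The share is f in Group 1 and 0 in Group 2, so the difference is f.

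| Scenario | f = 5% | f = 10% | f = 20% |
|---|---|---|---|
| Re-draw until Group 1 | 0.095d | 0.182d | 0.333d |
| One re-draw | 0.048d | 0.090d | 0.162d |
| Decline, not analysed | 0.050d | 0.100d | 0.200d |

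With d = 0.5 SD, the smallest entry is 0.048 × 0.5 = 0.024 SD and the largest is 0.333 × 0.5 = 0.167 SD.

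These formulas ignore the finite pool. I simulated a balanced pool that is fully used, with opened envelopes returned on a re-draw, at f = 20%. Re-drawing until Group 1 gives about 0.33d with 40 patients and 0.37d with 400. One re-draw gives about 0.15d in both. The sizes 40 and 400 are illustrative only. The order of magnitude does not change.

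Analysing everyone by the first envelope opened, with outcomes obtained, brings the composition bias to 0. Under re-drawing until Group 1, a fraction f of those first allocated to Group 2 would have exercised early, so the month-1 contrast would be diluted by f, that is by 5% to 20%.

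**3. Whether d bears on the planned comparison.** The analysis compares trends from baseline. If refusers differ from others by a constant L in OA level, and b is the imbalance in shares, the group difference is shifted by bL at baseline and by bL at 1 month. The shift in the comparison of change is bL − bL = 0. Only a difference in change of OA survives. The range above therefore applies to the trend comparison only if d = 0.5 SD is a difference in change, which is a stronger assumption than a difference in level.

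**The case for a change.** The strongest case for acting is that the gaps compound. The patient and whoever opens the envelope learn the allocation at once, the regimen is offered, no rule covers refusal, and no record is described that would show a second draw. Measuring OA at baseline does not help if keen patients improve faster. A log and a sentence on analysis as allocated would cost almost nothing.

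Part of this stands. From the text alone, a reader cannot verify that every draw was kept, and the text does not say that patients are analysed in the group first drawn. The rest does not carry to a change in the plan:

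- The text speaks of one envelope and one allocated regimen per patient and then describes delivery. Reading a re-draw into it rests on a single verb.
- Records may exist that so brief a document does not mention.
- Both groups receive the exercise regimen within the two months, so a patient who draws Group 2 waits a month and does not lose the treatment. The incentive to re-draw is weak.
- Replacing patient choice with a fixed order is not needed to gain verification, because a log and a no-reuse rule work equally well with patient choice. A fixed order also creates a next envelope that must be kept from those who enrol.
- An unnamed analysis population can occur under any randomisation method. Analysing patients in the group to which they were randomised is what a competent analyst would do by default.

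**Conclusion.** No change to the plan is called for. Followed as written, the procedure gives a concealed and potentially fully random allocation. The absent log, no-reuse rule and as-allocated wording are missing description, of a kind that trial staff and analysts ordinarily fill sensibly. No re-draw, refusal, imbalance or bias is shown.

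If re-draws or unanalysed refusals did occur, the distortion would be about 0.02 to 0.17 SD. That rests on an assumed refusal share of 5% to 20%, an assumed 0.5 SD difference in OA change between refusers and others, and approximately independent 1:1 draws. With no refusals, with refusers differing only in OA level, or with everyone analysed by first envelope and outcomes obtained, this composition bias is zero.

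The plan dates the study "between March 2017 - January 2019" and is written in the past tense, so a new allocation method would probably come too late in any case. What remains is an optional courtesy to readers of the trial report: the numbers of envelopes prepared, opened, declined and unused per group, as far as records allow, and confirmation that patients were analysed in the group of the first envelope opened.

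### As written, Group 2 is shown the exercises (and may get the manual) at baseline, before its no-exercise month, because delivery is not staged by group

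*Combined protocol and SAP*

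**What the plan says.** The Study Protocol section sets a different order of treatment for each group. For Group 1, "Group 1 was given exercise regimen and oral hygiene care advices for the first one month", with exercise then stopped. For the other arm, "Group 2 received oral hygiene care advices for the first one month, followed by the exercise regimen twice a day". Allocation is by an envelope opened with the patient after consent, so patients know their group from the start.

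The teaching is described once, for everyone: "The exercise program was demonstrated to patients by a clinician at the first visit and given to all patients printed as a manual". The clause about the manual reads in full "given to all patients printed as a manual to be done every day for one month duration of the exercise program". A diary for marking completed exercise and noting pain is also handed out, with no group or start date given.

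The same section mentions the first visit in two other places: "Patients' sociodemographic properties were recorded at the first visit" and "Oral care advices were given to every participant by a dentist involved in the study at their first visit". OA is "measured at baseline, 1-month, and 2-months by an experienced dentist at the faculty of dentistry", and that dentist is blind to the exercise regimens.

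**The concern.** The section staggers when each group exercises but not when each group is taught. If the demonstration is given to all patients at baseline, Group 2 learns the programme and is then expected to leave it alone for a month. These patients have the condition the exercises are meant to treat, know that exercise is coming, and can do it at home without equipment or supervision being mentioned. The plan records no instruction to refrain and no check on whether they did.

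The comparison at stake is the month-1 difference. In month 2 Group 1 has already exercised, so any comparison there is open to carry-over. Month 1 is the only randomised exercise-versus-none contrast without that problem. Early exercise that works would raise Group 2's 1-month OA, with two results:

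- the month-1 between-group difference shrinks towards zero;
- Group 2 starts its own exercise month from a higher value, so its measured gain in that month is smaller. This bears on the stated reason for the delayed-start design, which is to have more exercised patients to analyse.

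A further point is that the two exercise months may not be delivered alike. Group 1 starts straight after being shown the programme. Group 2 may start about a month after the only demonstration described.

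**Working it through.** The plan gives no sample size, effect size, standard deviation or early-exercise rate, so there is no figure of its own to reproduce. The check is mainly a reading of the text.

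**Step 1: what the first visit means.** The term occurs three times in the Study Protocol section.

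| Event | Recipients named | Timing implied |
|---|---|---|
| Sociodemographic data recorded | Patients | Baseline, by its nature |
| Oral care advice | Every participant | Baseline, since Group 2 needs it from the start of month 1 |
| Exercise demonstration | Patients, no group named | Baseline, if the term is used consistently |

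**Step 2: is a later session for Group 2 described?** No. Neither the Study Protocol section nor the Statistical analysis section mentions a demonstration, refresher or hand-out at 1 month.

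**Step 3: the manual.** It goes to all patients, but the visit is attached directly only to the demonstration. The rest of the clause ties the manual to the exercise month, so it could have been handed out when each group began. Its date for Group 2 is therefore uncertain.

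**Step 4: is early exercise checked?** The diary might have captured it, but the plan does not say when Group 2 received the diary or that month-1 entries were reviewed.

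**Step 5: illustration of size.** All inputs here are assumed. Let d be the full one-month gain from exercise, assume the effect is proportional to dose, and let

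q = (share of Group 2 exercising early) × (share of the full dose done).

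Group 2 then gains q × d in month 1, and the between-group difference becomes d − q × d = (1 − q) × d.

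| Share exercising early | Dose | q | Month-1 contrast kept | Lost |
|---|---|---|---|---|
| 0 | – | 0 | 100% | 0% |
| 0.10 | 0.5 | 0.05 | 95% | 5% |
| 0.25 | 0.5 | 0.125 | 87.5% | 12.5% |
| 0.25 | 1 | 0.25 | 75% | 25% |

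If Group 2's total gain by 2 months stays at d despite the early start, its gain in its own exercise month is also d − q × d = (1 − q) × d, so the same percentages apply.

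These figures describe the simple month-1 difference. They do not quantify the effect on the repeated-measurements analysis named in the Statistical analysis section, and they say nothing about power.

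**Step 6: gap from demonstration to start.** Group 1: 0 days. Group 2: 365.25 / 12 = 30.4, or about 30 days if there was no refresher; 0 days if the programme was shown again at 1 month.

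**The case against.** The strongest reply is that this is loose wording. Patients were offered their allocated regimen, and Group 2's regimen in month 1 was oral hygiene advice. The oral care sentence speaks of every participant, whereas the demonstration sentence speaks only of patients, which could mean those about to start exercise. That reading is possible, but it is less natural: the text does not state it, and both other uses of the term point to baseline.

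The diary cuts two ways. If all patients received everything at baseline, Group 2 also held a daily record in which early exercise could appear. If the diary was staged, a staged demonstration becomes more plausible. This softens the point without removing it, because neither the diary's start date for Group 2 nor any review of entries is described.

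Three further objections stand:

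- Being taught is not the same as exercising, and no early exercise is documented.
- Any bias is towards zero, so it could not explain away a positive result. Some risk of early exercise also comes with any delayed-start design in which patients know their group.
- The percentages rest on assumption alone, and the 30-day gap matters less if patients had a manual to remind them.

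Finally, the document is in the past tense and gives a study period ending in January 2019, so parts of the remedy may come too late. That limits what can be done now; it does not make the delivery rule sound.

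**Conclusion.** The concern holds as a design weakness worth considering, with medium confidence. Followed as written, the plan teaches the delayed group its home exercises before the month in which it serves as the no-exercise control. The conclusion rests on reading the first visit as baseline throughout the section and on the absence of any described later session. It is firm for the demonstration and only possible for the manual.

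Contamination is not established. If nobody in Group 2 exercised early, nothing is lost. If some did, the month-1 contrast is understated; the illustrated loss of 0% to 25% depends wholly on the assumed shares, dose-proportionality and, for Group 2's own exercise month, a fixed 2-month gain. The percentages show the direction and form of the problem and are not evidence of its importance in this trial.

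**What to change.** Tie delivery to each group's own exercise month. Group 1 gets the demonstration and manual at the first visit. Group 2 gets them at 1 month, after OA has been recorded and out of sight of the measuring dentist.

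At that 1-month point, someone other than the dentist should ask Group 2 once whether they did any mouth exercises in the preceding month. Asking after the reading cannot prompt exercise before it. A month-1 diary for Group 2 is optional, since it could itself encourage exercise.

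For this trial, if delivery was in fact staged, one sentence in the Study Protocol section saying so settles the matter. If everyone was taught at baseline, say that and report any month-1 exercise known in Group 2, including diary entries if they exist.

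The cost is one sentence of text and a moved session. A clinician must be available at 1 month. Because OA is measured at the faculty of dentistry while the study runs in the rheumatology outpatient clinic, Group 2 may need an extra clinic stop. The teaching must also be kept away from the dentist to preserve blinding.
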